Together the Co-PI's [name] and [name] conducted the first comprehensive investigation of the RAAS in HIV. Initial data revealed increased urinary aldosterone in HIV vs. controls in association with increased visceral adipose tissue (VAT) and HbA1c.⁶⁰ New published data from the Co-PIs further suggests that HIV subjects with relative increases in abdominal fat accumulation demonstrate significantly increased RAAS activation under standardized dietary and posture conditions. Also, increases in aldosterone are associated with insulin resistance.⁶¹ Furthermore, markers of inflammation, including hsCRP and IL-6, are increased under conditions of RAAS activation among HIV patients. Indeed, these novel studies performed in HIV serve as a paradigm to suggest a previously unexplored mechanism through RAAS activation by which HIV patients with an adverse metabolic phenotype are predisposed to CVD. Indeed, increased VAT is a predictor of subclinical CVD in HIV⁶² and, this proposal will test the hypothesis that increases in RAAS activation contributes to CVD in HIV. We will obtain novel information on the link between RAAS activation and myocardial and vascular injury in HIV through these studies. To that end, other studies have indicated that aldosterone levels independently correlate with CV mortality.^{63,64} Importantly, we will assess for the first time in HIV the specific contribution of MR signaling to multiple cardiac endpoints, including impaired CFR, myocardial fibrosis, diastolic dysfunction, and subclinical atherosclerosis, by applying MR blockade in an interventional trial among HIV patients selected based on the presence of metabolic abnormalities associated with RAAS activation and related subclinical atherosclerosis.

Summary and Implications: MR signaling may have an adverse role in CVD through vascular dysfunction, abnormal collagen deposition, vascular and myocardial inflammation, and increased oxidative stress⁶⁵. The burden of structural and functional

MIneralocorticoid Receptor Antagonism for CardiovascuLar hEalth in HIV The MIRACLE HIV Study

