heart disease in HIV is greater compared to the general population. We have demonstrated significant RAAS activation in HIV patients with metabolic abnormalities, including increased visceral adiposity and insulin resistance, and suggest that this unique physiology may contribute to a metabolic phenotype that is pro-inflammatory, pro-fibrotic, and pro-atherogenic. It is plausible that a cascade of excess MR activation in HIV potentiates cardiac injury and dysfunction. Moreover, there is relevant data to support testing the efficacy of MR blockade in managing impaired myocardial perfusion, myocardial fibrosis, diastolic dysfunction, and plaque. The grant will provide new mechanistic insight and enhance our understanding of CVD in HIV. We will take advantage of advanced imaging methods to permit a non-invasive longitudinal assessment of structural and functional CV defects in HIV to add new information to the field. This is an ideal proposal aiming to integrate several manifestations of CVD in HIV through a novel hormone pathway. The clinical utility of MR blockade could have far reaching effects towards overall CV risk reduction in HIV, and such studies could serve as a model for other at-risk metabolic groups.

II. Specific Aims

We will perform a randomized double-blind study among HIV subjects with increased visceral adiposity and subclinical atherosclerosis, administering eplerenone vs. placebo for 12 months. We will provide all subjects with lifestyle modification throughout the study. We hypothesize that adding eplerenone to lifestyle modification will significantly improve key indices of cardiac structure and function.

Among the large population of HIV patients in whom we have shown renin-angiotensin-aldosterone activation and subclinical atherosclerosis, we will determine:

❖ **Specific Aim I: The effect of MR blockade on myocardial perfusion.**

We hypothesize:

- a) MR blockade will improve coronary flow reserve (CFR) on cardiac positron emission tomography (PET) or stress myocardial blood flow (sMBF) on cardiac magnetic resonance imaging (MRI).
- b) MR blockade will reduce markers of vascular dysfunction.

❖ **Specific Aim II: The effect of MR blockade on myocardial inflammation and fibrosis.** We hypothesize:

- a) MR blockade will reduce myocardial extracellular volume fraction, a measure of myocardial fibrosis and inflammation, assessed by serial myocardial T1 mapping cardiac magnetic resonance imaging (MRI).

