- b) MR blockade will improve markers of inflammation and immune activation.
- c) Reduced myocardial fibrosis and inflammation resulting from MR blockade will relate to improvements in diastolic dysfunction evaluated through diastolic strain by tagged myocardial imaging on cardiac MRI.

❖ **Specific Aim III: The effect of MR blockade on coronary plaque.**

We hypothesize:

- a) MR blockade will result in plaque regression and reduced high risk plaque Morphology on coronary computed tomography angiography (CTA).
- b) Baseline CFR will relate to coronary plaque features in HIV patients with subclinical atherosclerosis.
- c) Improvements in coronary plaque with MR blockade will relate to improvements in CFR and inflammation.

**Mineralocorticoid Receptor Antagonism for Cardiovascular Health in HIV
The MIRACLE HIV Study**

Optional Substudy--

❖ **Specific Aim IV: The effect of RAAS activation on systemic inflammation and specific indices of arterial inflammation.**

We hypothesize:

- a) Markers of systemic and arterial inflammation will be increased during the RAAS activated state (under carefully controlled conditions of sodium restriction) when compared to the RAAS suppressed state (under carefully controlled conditions of sodium loading).
- b) Higher serum aldosterone levels during the RAAS activated state (under carefully controlled conditions of sodium restriction) will be related to greater in situ arterial inflammation measured by aortic TBR using cardiac 2-deoxy-2-18F-Fluorodeoxyglucose Positron Emission Tomography/Computed Tomography (¹⁸F-FDG-PET/CT).

❖ **Specific Aim V: The effect of MR blockade on arterial inflammation.**

We hypothesize:

- a) Treatment with MR blockade for 12 months will reduce in situ arterial inflammation measured by aortic TBR using cardiac ¹⁸F-FDG-PET/CT.
- b) Treatment with MR will reduce markers of systemic and vascular inflammation.
- c) Changes in aortic TBR will be related to changes in markers of arterial inflammation.

Optional Study for those who do not qualify following both screen visits—

❖ **Specific Aim VI: The degree of inflammation and cardiometabolic disease among those with/without visceral fat and those with/without coronary plaque**

We hypothesize:

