- a) Worsening markers of inflammation and heart disease across the spectrum stratified by presence and absence of excess VAT and presence and absence of coronary plaque (i.e. increased worsening across the following groups: low VAT/absence of plaque, low VAT/presence of plaque, high VAT/absence of plaque, high VAT/presence of plaque).

III. Subject Selection

Inclusion/Exclusion:

Inclusion Criteria: Up to 160 HIV male and female subjects will be consented to achieve the number of evaluable subjects. 42 subjects will be consented for the optional study.

Subjects will be included for:

- 1) Ages 40-65 years
- 2) Antiretroviral use (ART) >12 months and viral load <100 copies/mL
- 3) VAT > 110cm²

Exclusion Criteria:

- 1) Antihypertensive use including, ACE Inhibitor, ARB, MR blockade, diuretic, potassium (K) supplementation; or BP > 140/90 mmHg. Stable use (>3 months) of beta-blockers or calcium channel blockers (CCB) (except verapamil) is allowed.
- 2) Unstable statin use <12 months. Stable use (>12 months) is allowed.
- 3) Use of full dose ritonavir, nelfinavir, clarithromycin, and other strong inhibitors of CYP3A4, as well as CYP3A4 inducers.
- 4) Continuous oral steroid use (equivalent to prednisone \geq 5 mg daily) within the last 3 months.

**MIneralocorticoid Receptor Antagonism for CardiovascuLar hEalth in HIV
The MIRACLE HIV Study**

- 5) Uncontrolled diabetes requiring insulin and/or HbA1c > 7.5%.
- 6) Creatinine (Cr) > 1.5 mg/dL or estimated GFR<60 mL/min/1.73m².
- 7) K > 5.5 mEq/L.
- 8) Hemoglobin < 10 g/dL.
- 9) Known liver disease or ALT >3x ULN.
- 10) History of congestive heart failure, stroke, myocardial infarction, or known coronary artery disease.
- 11) Pregnant, actively seeking pregnancy or breastfeeding. Women of childbearing age may be on a non-hormonal form of contraception.
- 12) Estrogen, progestin derivative, or other sex steroid use within last 3 months. Stable physiologic testosterone replacement (> 3 months) is acceptable.
- 13) Current bacterial or other infections.
- 14) Active substance abuse.
- 15) Significant radiation exposure over the course of the year prior to randomization (e.g., radiation therapy, PCI, catheter ablation of arrhythmia) within 12 months of randomization.
- 16) Previous reaction or contraindication to gadolinium.
- 17) Coronary artery luminal narrowing >70% on coronary CTA.

Source of subjects and recruitment methods:

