Upon confirmation of eligibility, subjects will be given the option through a formal consenting process to participate in the substudy prior to randomization. Participation in the main study will not be affected if subjects choose to decline participation in the substudy; however, subjects withdrawn from the main study will be withdrawn from the substudy.

If subjects do not qualify for the main study following completion of both screening visits, subjects will be given the option to participate in an optional blood sampling visit.

Treatment assignment and randomization:

During the Baseline Visit randomization will be done. Subjects will be randomized 1:1 to receive eplerenone PO 50mg daily or identical placebo for 12 months. The randomization list, stratified by gender, statin use, and presence of plaque will be generated by the biostatistician and kept by the research pharmacy. Daily dosing starts at 50 mg for the first week to avoid hypotension and will be increased to 50 mg twice daily at the 1 week safety visit. The study will be double-blinded. All subjects will receive lifestyle modification as described below.

Prior to randomization in all cases, the subject's primary care physician will be consulted regarding the appropriateness of the protocol including the lifestyle modification program with the subject's permission. Subjects are not eligible if they do not meet all of the enrollment criteria.

In the event that a subject wishes to withdraw from the study, the subject will be asked to return all unused study medication.

V. Study Procedures

Data Collection

Screening Visit 1 (to determine eligibility):

We will obtain:

- 1) Informed consent, history and physical, urine pregnancy test for females.
- 2) Blood for Cr, K, ALT, CBC, HbA1c, and HIV viral load.

Screening Visit 2 (to determine eligibility): Subjects will present after a 12 hr fast. If eligible from Screening Visit 1, we will obtain:

- 1) Urine pregnancy test for females as appropriate.
- 2) Coronary CTA for coronary plaque assessment. (This will not be performed if the subject has a previous reaction or contraindication to iodine-containing contrast media).
- 3) CT Abdomen for single slice screening at L4 for VAT determination.

Optional Blood Sampling Visit (For those who do not qualify after both screening visits): Subjects will present after an overnight 12 hr fast.

- 1) Fasting blood for markers of heart disease and inflammation

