Statistical algorithms as detailed in Aim I will be applied to these specific endpoints. Moreover, the relationship between baseline CFR and non-calcified plaque volume will be assessed. Lastly, we will also determine whether longitudinal changes in coronary plaque are associated with changes in biomarkers of inflammation and immune activation to understand the potential relationship of these inflammatory indices as markers of improved indices of the coronary vasculature in response to MR blockade in the HIV. **Sample Size Determination:** In our prior studies assessing plaque in HIV, the median [IQR] change of noncalcified plaque volume over 12 mos was $6.7[-6.5, 29.8]$ mm 3 .¹³ We assumed a conservative SD of 18mm 3 taking the mean of the IQR. This study enrolling 80 subjects with 68 evaluable subjects will attain 85% power at a two sided α of 0.05 to detect a difference in noncalcified plaque volume of 13.3mm 3 between eplerenone vs. placebo, a clinically relevant change. For biomarkers, this study has 85% power at a two-sided 0.05 α level to show a change of at least 0.74 SD after treatment with eplerenone vs. placebo.

Aim IV: For this aim, the endpoint is change in MCP-1 between the low sodium and liberal sodium diets. Secondary endpoints will include: change in hsCRP, pentraxin3, IL6, Lp-PLA $_2$, sCD14, sCD163. We will test the change in biomarkers between the RAAS activated (sodium restricted) and RAAS suppressed states (sodium loaded) using the paired Student's t-test for normally distributed variables or Wilcoxon signed-rank test for non-normally distributed variables. We will apply Pearson's correlation for variables that are normally distributed and Spearman's correlation for variables that are non-normally distributed to determine whether there is a significant correlation between aldosterone during the RAAS activated state and TBR. Covariates considered for inclusion in modeling include variables that may affect vascular dysfunction, inflammation, and plaque (age, race, sex, BP, tobacco/illicit drug use, family history of CVD, lipids, glucose), and HIV parameters (viral load, CD4, duration of HIV and ART use). This will permit us to assess relevant factors that may mediate the effect of aldosterone on inflammation in HIV and interactions between HIV and traditional risk factors contributing to inflammation. **Sample Size Determination:** Preliminary data in HIV presented in this

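### The aims describe subjects with subclinical atherosclerosis but entry does not require plaque, and the Aim III power of 85% counts all 68 evaluable subjects without stating how many are expected to have plaque or a CTA.

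*Combined protocol and SAP*

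**What the plan says.** Two places describe who is being studied. Section II (Specific Aims) announces a "randomized double-blind study among HIV subjects with increased visceral adiposity and subclinical atherosclerosis". Section I (Background and Significance) says the patients are "selected based on the presence of metabolic abnormalities associated with RAAS activation and related subclinical atherosclerosis". Aim III(b) also refers to patients with subclinical atherosclerosis.

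Section III (Subject Selection) lists three inclusion criteria: age 40-65, antiretroviral therapy for more than 12 months with viral load below 100 copies/mL, and visceral fat area above 110 cm². None concerns plaque. The only CTA-based criterion in that list is an upper limit, "Coronary artery luminal narrowing >70% on coronary CTA". Section IV (Treatment assignment and randomization) then specifies "The randomization list, stratified by gender, statin use, and presence of plaque", and section VI repeats the factor.

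On the CTA itself, section V says of both the screening scan and the end-of-study scan: "This will not be performed if the subject has a previous reaction or contraindication to iodine-containing contrast media". Contrast contraindication is not among the exclusion criteria in section III.

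Aim III hypothesises that "MR blockade will result in plaque regression and reduced high risk plaque Morphology". Its endpoint (section VI) is the change in noncalcified plaque volume. The sizing text says "This study enrolling 80 subjects with 68 evaluable subjects will attain 85% power" for a difference of 13.3 mm³, with an SD of 18 mm³ derived from a prior 12-month median change of 6.7 mm³ (IQR -6.5 to 29.8).

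**The concern.** The population named in the aims is not the one that the eligibility criteria admit. Stratifying on presence of plaque has a purpose only if some randomised subjects have none, and such subjects have no plaque to regress. Aim III still uses the same 68 as the flow reserve and extracellular volume aims. It borrows its variability from a study whose title in the reference list names patients with subclinical atherosclerosis. The plan states no expected plaque prevalence, no Aim III analysis set and no handling of zero baseline plaque.

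Two things are at stake. The first is whether the stated power describes the trial that will be run. The second is interpretation: a null Aim III result could reflect no effect or dilution, and a plaque-positive subset chosen after unblinding would be post hoc.

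**Working it through.** **Inputs from the plan (section VI).** 80 randomised 1:1, 15% attrition, so 80 × 0.85 = 68 evaluable, 34 per arm. Difference 13.3 mm³, SD 18 mm³, two-sided α 0.05. Source median change 6.7 mm³, IQR -6.5 to 29.8.

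**Assumed, because the documents give nothing.** The share with plaque, p, is taken as 90%, 75% and 50%. The control-arm mean change in carriers is taken as the source median, 6.7 mm³.

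**Step 1: the plan's figure.** The noncentrality is 13.3 / (18 × √(2/34)) = 13.3 / 4.37 = 3.05. Against a critical t of 1.997 on 66 df, power is 85.1%. The detectable difference at 85% is 13.28 mm³. The stated figure reproduces.

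**Step 2: 13.3 mm³ read as the effect in carriers, with no change in the others.** The whole-cohort difference is 13.3p. Within an arm whose carriers have mean change μ, the variance is p × 18² + p(1 - p)μ², with μ = 6.7 on placebo and 6.7 - 13.3 = -6.6 on eplerenone. The SD is the root of the average of the two variances. The carriers-only analysis uses 34p per arm with SD 18; fractional numbers are kept.

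| p | Difference, all 68 | SD, all 68 | Power, all 68 | Power, carriers only | Detectable difference in carriers |
|---|---|---|---|---|---|
| 100% | 13.3 | 18.0 | 85% | 85% | 13.3 mm³ |
| 90% | 11.97 | 17.2 | 81% | 81% | 14.0 mm³ |
| 75% | 9.98 | 15.9 | 72% | 73% | 15.4 mm³ |
| 50% | 6.65 | 13.2 | 54% | 55% | 19.1 mm³ |

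Restricting to carriers gains 0.4, 1.0 and 1.4 percentage points at 90%, 75% and 50%.

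**Step 3: 13.3 mm³ read as the whole-cohort difference.** The carrier effect must then be 13.3/p, that is 14.8, 17.7 and 26.6 mm³. With the same variance formula, power at 34 per arm is 88%, 92% and 96%.

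**Step 4: the SD.** The plan's 18 is half the IQR width: (29.8 + 6.5)/2 = 18.15. Under normality the SD is IQR/1.349 = 36.3/1.349 = 26.9. Power for 13.3 mm³ is then about 52% even if all 68 have plaque. Scaling the carriers-only detectable differences by 26.9/18 gives 14.0 → 20.9, 15.4 → 23.0 and 19.1 → 28.5 mm³.

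**Step 5: subjects without CTA.** They have no Aim III outcome and no scan on which to assign the plaque stratum. The documents give no expected number, so no loss is calculated for them.

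**The case against.** A reader might infer that 85% holds only if all 68 have plaque. The documents do not support that, for these reasons.

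- **Small shortfalls hardly matter.** With 65 of 68 carriers, power is still within two points of 85%.
- **The plan states a between-arm difference, not a carrier effect.** On the whole-cohort reading (Step 3) power does not fall. This stands. However, the carrier effect then has to grow as prevalence falls, and the plan neither states nor justifies that.
- **Plaque-free subjects can form plaque.** The endpoint is change in volume, which registers new plaque, and the source median is progression. As an illustration, suppose plaque-free controls gain 6.65 mm³, treated ones gain none, and the SD is 9 (all assumed). All-subject power is then about 82% at 75% with plaque and 80% at 50%. Zero change in both arms is therefore an unfavourable case, not a forecast.
- **Full prevalence would not secure 85% either,** because of the SD (Step 4).
- **The sizing text does not name its source population.** It mentions only prior plaque studies in HIV. The link to subclinical atherosclerosis is the title of the cited trial, and the arm or subset that supplied the figures is not shown.

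It is also fair that only Aim I is labelled primary, and that Aims I and II do not need plaque. Enrolling on visceral fat and stratifying by plaque is a defensible design. Section VII (CTA contrast medium) does say that subjects with contrast allergy are kept out of the CTA, but it does not adjust the Aim III number for them.

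What remains is the mismatch between described and eligible populations, and a sizing statement silent on prevalence, paired CTA and zero baseline plaque.

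**Conclusion.** The mismatch between the aims and eligibility is a plain reading of the text and needs no assumption. The passages must be reconciled.

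The power point is conditional. On the carrier-effect reading with no change in plaque-free subjects, 85% becomes about 81%, 72% and 54% at 90%, 75% and 50% with plaque. On the whole-cohort reading power is kept, at the price of an unstated larger effect in carriers. The plan does not say which reading it intends, and the prevalence is not in the documents. The supportable conclusion is that the 85% is unsupported as stated, not that it is shown to be wrong by a given amount. The SD of 18 adds to this: it is labelled conservative but is smaller than the normal conversion of its own source IQR.

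This should be corrected. It concerns a separately powered aim, though not the Aim I primary endpoint.

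**What to change.** 1. Reconcile the population described in sections I and II with the eligibility criteria in section III, so that both say whether plaque is required.
2. In the Aim III sizing, replace the blanket 68 with the expected number with paired CTA and, of those, the expected number with plaque. Say how subjects without a screening CTA are assigned to a plaque stratum and how zero baseline plaque is analysed.
3. State whether 13.3 mm³ is a whole-cohort or a carrier difference. Give the detectable difference in carriers over a stated prevalence range: at 90%, 75% and 50%, about 14.0, 15.4 and 19.1 mm³ with SD 18, and about 20.9, 23.0 and 28.5 mm³ with SD 26.9. Justify the SD chosen.
4. Keep the all-subject intention-to-treat comparison. Pre-specify the plaque-present randomisation stratum as the supporting analysis of the regression hypothesis. Making the stratum the main analysis is debatable: it gains less than 1.5 points of power in Step 2 and cannot register new plaque in subjects who start without any.

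The cost is a less favourable stated figure and one extra analysis. Because plaque is already a stratification factor, the within-stratum comparison stays randomised. No subjects or procedures are added.

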time x treatment interaction, which will provide unbiased effect estimate under missing at random condition, which will be carried out by using augmented data sets created by multiple imputation. A sensitivity analysis will be performed to include only those subjects who completed the study. Baseline variables will be compared between treatment groups, and any variable that is statistically different between groups will be controlled for using multivariable modeling. It may be that subjects with more significant RAAS activation and dysregulation in aldosterone at baseline) are more responsive to eplerenone. We will phenotype the RAAS in subjects at the low sodium visit and, guided by this data, may use aldosterone levels prior to intervention as an index of RAAS activation and a covariate in assessing treatment response, to determine if eplerenone is more effective in the subpopulation with greater baseline aldosterone dysregulation and RAAS activation. Covariates that will be considered for inclusion in modeling, include variables that differ at baseline and those variables that may affect vascular dysfunction, inflammation, fibrosis and plaque (age, race, gender, BP, tobacco/illicit drug use, family history of CVD, lipids, and glucose), HIV parameters (viral load, CD4, and duration of HIV and ART use) and compliance. This will permit us to assess relevant factors that may mediate the effect of eplerenone on CFR in HIV and interactions between HIV and traditional risk factors contributing to eplerenone effects. Moreover, we will compare changes in CFR and vascular biomarkers over 12 months using regression analysis. We will perform Pearson's correlation for variables that are normally distributed and Spearman's correlation for variables that are non-normally distributed. If we see significant changes in specific biomarkers that correlate with changes in CFR, then we will run those specific biomarkers from stored serum at earlier time points (e.g. 6 months) to see if early changes in biomarkers can predict changes in CFR, as well as predict response to MR blockade. **Biostatistician Role:** The biostatistician will monitor data collection, quality and completeness of the study throughout all years of the grant. The biostatistician will create the randomization plan, using a permuted block algorithm, stratified for gender, statin use, and presence of plaque and provide the list to the study pharmacist (investigators will remain blinded). Identical placebo will be provided by the pharmacy. **Sample Size Determination:** Preliminary data from HIV subjects presented in this grant demonstrate a CFR 1.74 ± 0.73 (mean \pm SD) using cardiac PET. Supportive data are also derived from a longitudinal study by our team using cardiac PET, showing mean \pm SD change of CFR in diabetics treated with spironolactone 0.33 ± 0.83 vs. placebo: 0.02 ± 1.03 over 6 months (mean SD=0.93).⁴⁰ Given these data, we considered the range 0.73 - 0.93 SD to accurately reflect the potential variability of change in CFR for the proposed study. Based on this data, we now provide a range of detectable differences using 85% power and a revised increased sample size of 80 subjects, with an attrition rate of 15%, leaving 68 evaluable subjects. Thus, even choosing a conservative SD of 0.93, the study will be well powered to detect a difference in mean change of CFR of at least 0.69. As our preliminary data, using PET, show that HIV patients have a mean CFR 1.7, an increase of CFR to 2.4 with eplerenone is a clinically relevant increase associated with decreased morbidity and mortality. For the sMBF and biomarkers, this study has 85% power at a two-sided 0.05 α level to show a change in the variable of at least 0.74 SD after treatment with eplerenone vs. placebo.

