Aim VI: In an exploratory analysis, subjects will be enrolled using a factorial sampling strategy into 4 analytic strata (low VAT/absence of plaque, low VAT/presence of plaque, high VAT/absence of plaque, high VAT/presence of plaque). Using this design, we will first analyze whether there are differences in markers of inflammation and heart disease by VAT status (main effects model comparing presence and absence of excess VAT) using student's t-test for variables that are normally distributed or Wilcoxon rank sum test for variables that are not normally distributed. Based on the exclusion criteria excess VAT is determined to be $>110\text{cm}^2$. After assessing for differences in VAT in the main effects model, we will examine the degree to which markers of inflammation and heart disease are related to coronary plaque in both the high and low VAT groups, and whether this relationship is stronger in the coronary plaque group as a result of increased VAT using ANOVA for variable that are normally distributed and Kruskal-Wallis Test for variables that are not normally distributed.

VII. Risks and Discomforts

Blood Drawing: The total blood drawn for subjects completing the study is equivalent to approximately 560 ml (over a period of 12 months). This quantity of blood drawing does not pose excessive risk to subjects. By comparison, the Red Cross allows a healthy adult to donate 1 pint of blood every 8 weeks, which is about 473 ml. Subjects with a hemoglobin < 10 mg/dL will be excluded from the study. There will be minimal risk and

Mineralocorticoid Receptor Antagonism for Cardiovascular Health in HIV The MIRACLE HIV Study

discomfort associated with blood drawing and IV placement. The risks of these procedures are minor bruising or bleeding at the site of the blood draw or IV catheter or feeling faint. Standard clean insertion techniques will be utilized to minimize risk of infection.

Intravenous Catheter Placement: There are minor risks and discomforts associated with having an intravenous line and with injection of contrast agent through the intravenous line, including the possibility of bleeding, pain, inflammation (redness and swelling), and leaking of contrast agent outside of the vein at the site of the IV. These problems usually self-resolve or only require minor treatments, such as application of an ice-pack or slight pressure for a few minutes.

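### Aim VI compares markers across observed VAT and plaque groups with unadjusted tests only, so it cannot support its own wording that attributes a stronger plaque relationship to visceral fat

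*Combined protocol and SAP*

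**What the plan says.** Section II states the Aim VI hypothesis: "Worsening markers of inflammation and heart disease across the spectrum stratified by presence and absence of excess VAT" and of coronary plaque, in four ordered groups. Section IV gives the source of participants for the optional blood visit: "If subjects do not qualify for the main study following completion of both screening visits, subjects will be given the option" to give that sample.

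Section VI, Aim VI contains the whole analysis. It begins "In an exploratory analysis, subjects will be enrolled using a factorial sampling strategy into 4 analytic strata". VAT status is compared first, in what is called a "main effects model comparing presence and absence of excess VAT", by "student's t-test for variables that are normally distributed or Wilcoxon rank sum test for variables that are not normally distributed". Plaque is then examined in the high and low VAT groups, together with "whether this relationship is stronger in the coronary plaque group as a result of increased VAT", by "ANOVA for variable that are normally distributed and Kruskal-Wallis Test for variables that are not normally distributed". The paragraph names no covariate, regression model or matching, and it gives no sample size.

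The other aims differ. Aim I plans multivariable models that consider "variables that may affect vascular dysfunction, inflammation, fibrosis and plaque (age, race, gender, BP, tobacco/illicit drug use" and further items. Aims II, III and V adopt the Aim I methods by reference. Aim IV has its own similar list. Statin use is a randomisation stratum but is in none of these lists.

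**The concern.** Aims I, II, III and V compare randomised arms, and the main test in Aim IV is within person. Aim VI has neither protection and is also the only aim without covariate modelling. Sampling by VAT and plaque defines the four strata but does not balance age, sex, smoking or statin use across them.

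If those characteristics differ between groups and also move the markers, an unadjusted test can show a difference where VAT or plaque contributes nothing. It can also hide a real one, for example if people with plaque use statins more often and statins lower the marker. At stake is how the Aim VI results are interpreted, above all the clause that attributes a stronger plaque relationship to VAT.

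**Working it through.** **1. Is adjustment planned anywhere for Aim VI?** Aim I has it; Aims II, III and V import it; Aim IV restates it. Aim VI does neither. The test called a main effects model is a two-group comparison on VAT that does not adjust even for plaque, the other sampling factor. No interaction term is named, although the second question is one of effect modification.

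**2. Does the plan name plausible confounders?** Yes. The Aim I and Aim IV lists include age, sex (or gender) and tobacco among variables that may affect inflammation and plaque, which are the outcome and one exposure of Aim VI.

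**3. How large could the bias be?** Aim VI states no figure to reproduce and the documents give no inputs, so everything below is assumed.

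*Plaque.* Age is uniform on 40-65 (the entry range), so its SD is 25/√12 = 7.22 years. Smoking prevalence is 40%. The log-odds of plaque are 0.8 per SD of age and 0.8 for smoking, which makes the plaque group about 5 years older. The marker changes by 0.2-0.3 SD per SD of age and by 0.3-0.5 SD with smoking. There is no true plaque effect.

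Spurious difference = age slope × age gap in SD + smoking effect × smoking gap.

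- Age gap: 5/7.22 = 0.69 SD.
- Lower setting, simulated total 0.19 SD: age gives 0.2 × 0.69 = 0.14, leaving 0.05 for smoking, which is a smoking gap of 0.05/0.3 ≈ 0.17.
- Upper setting: 0.3 × 0.69 + 0.5 × 0.17 = 0.21 + 0.08 = 0.29 (simulated 0.30).
- Lower setting with statin use of 40% vs 20% and a 0.4 SD lowering effect: 0.19 − 0.4 × 0.20 = 0.11 (simulated 0.11-0.12). The net bias therefore depends on the mix of confounders.

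Rejection rates at two-sided 0.05, without the statin term (4,000 runs per setting; two equal VAT groups, independent of the confounders):

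| Test | n=42 | n=122 |
|---|---|---|
| Four-group ANOVA | about 7-10% | about 11-21% |
| Plaque comparison within one VAT group | about 7-9% | about 10-19% |
| Linear model adjusted for the confounders | about 5% | about 5% |

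Both sample sizes are assumptions. Section III gives 42 for the optional study, but 42 is also the Aim IV/V substudy size. The 122 adds the 80 main-study subjects (42 + 80).

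*VAT.* Here the planned test is itself a two-group comparison. Take one binary confounder that shifts the marker by g SD, with prevalence p0 in low VAT and p1 in high VAT, and no true VAT effect. The spurious difference is g × (p1 − p0):

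- 0.5 × (0.5 − 0.3) = 0.10 SD at the mild end.
- 0.8 × (0.7 − 0.2) = 0.40 SD at the strong end.

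Across this range the unadjusted t-test rejects 6-23% of the time at N=42, 7-39% at N=80 and 9-66% at N=160. Adjusted, it stays at about 5%. With equal prevalence in both groups the unadjusted test also stays near 5%.

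**The case against.** The strongest reply is that Aim VI is labelled exploratory, rests on an optional blood draw, states no alpha or power, and does not bear on the randomised treatment comparison. Simple group comparisons are an ordinary first step, and a descriptive gradient across four groups can be reported without adjustment. This stands as a limit on importance. It does not rescue the clause that attributes a stronger relationship to VAT, because calling an analysis exploratory does not remove bias.

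Entry criteria narrow the confounding: age is restricted, and uncontrolled diabetes, raised blood pressure, recent statin changes and known coronary disease are excluded. This also stands in part, but smoking, sex and age within the range can still differ.

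Four stronger readings are tempting, and the documents do not support them:

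- *That differences will be presented as effects of both VAT and plaque.* For plaque the text speaks only of a relation. The causal wording concerns VAT.
- *That every variable in the Aim I list is a confounder here.* The list gives candidates for inclusion and does not mention VAT. Section I ties visceral fat to HbA1c and insulin resistance, so glucose may lie on the pathway from VAT.
- *That the false-positive rate for plaque is 9-15% at n=42 and 17-33% at n=122.* Those rates come from the same assumed inputs but with a two-group t-test pooled over VAT, which is not the test planned for plaque.
- *That 42 is the Aim VI sample size.* The documents do not establish this.

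**Conclusion.** The point holds in a limited form. The only tests written for Aim VI are unadjusted comparisons of observed groups, so differences may partly reflect age, sex, smoking or statin use. They cannot support a statement that anything is due to increased VAT. Neither the size nor the direction of the net bias can be known from the documents, and if the groups happen to be balanced there is none. The simulated error rates show that the mechanism is material under plausible but assumed inputs; they do not estimate what this study will find. A reader might infer that the trial's efficacy conclusions are weakened. They are not: the consequence is confined to the interpretation of Aim VI.

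**What to change.** In Section VI, Aim VI, make the main analysis one linear model per marker, transformed where skewed, with VAT, plaque and VAT-by-plaque interaction terms, adjusted for a fixed set of covariates: age, sex, current smoking and statin use. The interaction is needed to address whether the plaque relationship is stronger with high VAT. Report the adjusted contrasts as the Aim VI result, keep the planned unadjusted tests as description, and replace the causal phrase with a statement of association.

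The cost is mainly wording. Age and statin use are needed to determine eligibility, and a history is taken at Screening Visit 1. That this history records current smoking is an inference and should be confirmed. The statistical cost is four degrees of freedom: with the assumed n=42, residual degrees of freedom fall from 42 − 4 = 38 (four group means) to 42 − 8 = 34. Residual confounding by unmeasured factors would remain, which is a further reason for associational wording.
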